10.2 Other Endpoints

a. Cancer relapse (clinical): Time from registration to documented invasive local or regional recurrence will be assessed using the **S1415CD** 6 Month Status Update and the **S1415CD** 12 Month Status Update. Invasive recurrence includes local, regional, or distant recurrence with histological confirmation preferred. Applies only to patients with local or regional disease treated with curative intent. Relapse will not be assessed for persons with metastatic disease at diagnosis. This endpoint will be monitored because it may affect the likelihood of allowing a full dose of systemic therapy, but is not tied to a formal hypothesis because of the small expected number of events.

10.3 Performance Status:

Patients will be graded according to the Zubrod Performance Status Scale.

POINT DESCRIPTION

0 Fully active, able to carry on all pre-disease performance without restriction.

1 Restricted in physically strenuous activity but ambulatory and able to carry out work of a light or sedentary nature, e.g., light housework, office work.

2 Ambulatory and capable of self-care but unable to carry out any work activities; up and about more than 50% of waking hours.

3 Capable of limited self-care, confined to bed or chair more than 50% of waking hours.

4 Completely disabled; cannot carry on any self-care; totally confined to bed or chair.

11.0 STATISTICAL CONSIDERATIONS

11.1 Estimate of Sample Size

Because FN events are less common in the intermediate risk group, we calculated sample size by taking a 2-step approach, working backwards from Primary Objective c to Primary Objective b and then demonstrating that Primary Objective a will have adequate power. For Primary Objective c, we fixed power at 80% and the number of components at 24 (12 for PP-CSF, 12 for no PP-CSF). For these parameters, we obtained the sample size required in the Intervention arm to test the primary hypothesis for Primary Objective c: a 50% reduction in FN occurrence between the experimental (PP-CSF) and control (no PP-CSF) arms among patients receiving intermediate risk chemotherapy (measured by the odds ratio). Using this sample size, we determined the number of components needed in the Usual Care arm to give us at least 90% power to detect a 50% reduction in Primary Objective b.

Step 1: For Primary Objective c, data used to inform the sample size calculations include: the risk of FN among control patients observed in retrospective studies (15%); and the

relative proportions of patients with breast, lung, and colorectal cancer receiving intermediate risk chemotherapy. (44,45,46,47,48) The null hypothesis used for determining sample size is that there will be no difference in FN incidence within 6 months from registration (i.e., initiation of chemotherapy) between intervention and control groups.

Sample size estimates for the intermediate risk group are based on a 50% reduction in the FN rate (the reduction observed in trials for high risk settings). This translates to a reduction in FN rate from 15% to 7.5%, when comparing intermediate risk control arm patients (no PP-CSF) to intermediate risk intervention arm patients (PP-CSF). We believe this is reasonable because the one prospective trial evaluating PP-CSF for intermediate risk chemotherapy given to women with breast cancer achieved a risk reduction of 90%, and a systematic review of clinical trials of PP-CSF use in several settings found an FN rate reduction ranging from 17% to 78%. (49) To account for possible correlation between patients within components we estimate an intraclass correlation coefficient (ICC) of 0.02. An ICC of zero corresponds to randomization of individuals rather than components; $ICC > 0$ indicates patient outcomes are more similar within a component than across components. We estimated the ICC for FN in the SWOG adjuvant breast cancer study **S0221** which has 262 clinics with 2,666 patients. (50) Using a random effects logistic regression program (component is the random effect) followed by numerical integration, the ICC was estimated to be 0.01 although statistically significantly greater than zero. We are using 0.02 to protect against underestimation of the ICC. Based on a two-sided 0.05 alpha level test, 24 components in the Intervention arm (12 components randomized to PP-CSF and 12 components to no PP-CSF among intermediate risk patients) and 45 intermediate-risk patients per component on average will give 80% power to detect whether PP-CSF reduces FN rate by 50% among patients receiving intermediate risk chemotherapy. We assume that high, intermediate and low risk patients comprise 30%, 50% and 20% at each component, respectively; this translates to a total of 90 patients per component on average. (51,52)

Step 2: Consider the hypothesis of [Primary Objective b](#): a relative reduction in FN occurrence over 6 months from registration between the Intervention and Usual Care arms (measured by the odds ratio) over both high and intermediate risk groups. We assume FN risk of 25% for the high risk chemotherapy group (translating to a reduction in FN rate from 25% to 12.5%). Using the sample size calculations from Step 1, we employ a 3:1 randomization scheme in the main trial, resulting in 8 components randomized to Usual Care and 24 components randomized to Intervention. This translates to a total of 2,880 patients, 32 components (90 patients per component on average) for the study, and gives us 90% power for [Primary Objective b](#): to detect a 50% reduction in FN events among high and intermediate risk patients in components randomized to the guideline-based PP-CSF order Intervention vs. Usual Care. [Figure 1](#) displays a power curve for our first and second Primary Objectives.

[figure not shown]

Figure 1: Power with respect to the reduction in FN rate. The dashed vertical line is at 50% reduction. The two dashed horizontal lines are at 80% and 90% power.

Table 2 below illustrates how the required sample size for [Primary Objective c](#) and corresponding power for [Primary Objective a](#) vary according to the ICC.

Table 2. Power to detect 50% relative reduction in the FN rate. Power depends on control arm event rate and ICC.

Intra-Class Correlation	Total Sample Size	Per arm sample size		Per arm # of components		Per component sample size		Power	
		Usual Care	Order Entry	Usual Care	Order Entry	Usual Care	Order Entry	Primary Obj b	Primary Obj a
0	1536	384	1152	8	24	48	48	80%	98%
.01	1984	496	1488	8	24	62	62	80%	94%
.02	2880	720	2160	8	24	90	90	80%	90%
.03	5376	1344	4032	8	24	168	168	80%	86%

Using this sample size and with greater than 80% power, we can detect the following effect of Intervention versus Usual Care in the process outcomes of [Primary Objective a](#), namely the proportions of patients using CSF as primary prophylaxis versus other use: a reduction in CSF use from 17% to 7% among low risk patients and an increase in CSF use from 40% to 75% among high-risk patients (based on observed use in our prior observational study). (53)

In addition to the 32 study components, we will include 13 components with existing PP-CSF order entry systems in the parallel cohort to recruit 720 patients (56 patients per component on average).

A total of 3,600 eligible patients will be included in the study over a 2.75 year accrual period: 2,160 for the Intervention arm; 720 for the Usual Care arm; and 720 for the Cohort. We will allow for 10% additional accrual for a total of 3,960 patients. On average, this translates to 99 patients per component in the RCT, and 60 patients per component in the Cohort. We will allow the maximum total number of patients per site to be flexible (i.e. not capping accrual at 99 patients per site), in order to allow high-accruing sites to compensate for low-accruing sites, and ultimately allow us to reach our total required sample size of 3,960 patients for the study. This total will account for ineligible patients, as well as dropout and death (not due to FN) that may occur earlier than 6 months after registration and therefore act as a competing event with FN occurrence. Additionally, we will monitor accrual to ensure that our assumed distribution of 30% high, 50% intermediate and 20% low risk patients in the overall sample across all components is roughly maintained. Major deviations from this assumption could result in a loss of power, and therefore if such deviations are observed, we will consider capping accrual by regimen risk.

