1.0 OBJECTIVES

1.1 Primary Objective(s)

- a. To compare the use of primary prophylactic colony stimulating factor (PP-CSF) according to recommended clinical practice guidelines among patients registered at Intervention components versus Usual Care components.
- b. To compare the rate of febrile neutropenia (FN) among patients registered at Intervention components versus Usual Care components.
- c. To compare the rate of FN among intermediate risk patients registered at Intervention components by component treatment assignment (administer PP-CSF to intermediate risk patients versus not).

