11.5 Intent-to-Treat Analysis

There may be non-compliance at the component level in the primary randomization and at the component or patient level in the secondary randomization. The primary analysis will be an intent-to-treat (ITT) analysis, which will disregard non-compliance and analyze patients and components according to the groups to which they were randomly assigned. As a sensitivity analysis, we will account for non-compliance and conduct an as-treated analysis. In order to understand any differences between results from the ITT and as-treated analyses and to assess the extent to which crossover components and patients may have biased results, we will compare their characteristics to those of all other components and patients in the analysis.

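### For the intermediate-risk randomization, the only planned effect estimate that accounts for changed orders is as-treated (Section 11.5); a randomization-based complier estimate should sit beside it

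*Combined protocol and SAP*

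**What the plan says.** Section 1.1 defines Objective c as a comparison of FN among intermediate-risk patients "registered at Intervention components by component treatment assignment (administer PP-CSF to intermediate risk patients versus not". Section 11.1 sizes it for "a 50% reduction in FN occurrence between the experimental (PP-CSF) and control (no PP-CSF) arms", that is 15% versus 7.5%, with 12 components per group, 45 intermediate-risk patients per component, ICC 0.02 and two-sided 0.05, for 80% power. On the source of the effect it says "Sample size estimates for the intermediate risk group are based on a 50% reduction in the FN rate (the reduction observed in trials", the trials being those in high-risk settings.

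What is randomized is a default order. Sections 7.1 and 11.2 leave physicians free to change any patient's orders at any time. Section 11.5 expects this: "There may be non-compliance at the component level in the primary randomization and at the component or patient level in the secondary randomization". It makes ITT primary, adds an as-treated sensitivity analysis, and plans a comparison of the characteristics of crossover components and patients with those of the rest. No other FN effect estimate that accounts for non-compliance is described.

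**The concern.** Objective c is meant to fill an evidence gap about PP-CSF itself (Section 2.0), but the ITT result estimates the effect of a default. A reader will also want the effect of receiving PP-CSF, and the plan offers only an as-treated answer.

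That analysis gives up the randomization. Section 2.0 notes that most guidelines ask clinicians to weigh age, comorbid illness and similar factors alongside the regimen. Section 7.3 says the algorithm is based on the regimen alone. A physician who overrides the default may therefore be responding to the patient's own FN risk. Patients given PP-CSF against a no-PP-CSF default would then tend to be at higher risk, and patients left without it against a PP-CSF default at lower risk. Either pattern makes PP-CSF look worse than it is.

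**Working it through.** **1. The plan's 80%.** Inputs from Section 11.1: 12 components per group, 45 patients each, ICC 0.02, 15% versus 7.5%, two-sided 0.05.

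- Design effect = 1 + 44 × 0.02 = 1.88.
- Effective n per group = 12 × 45 / 1.88 = 287.2.
- Power: 81.3% (pooled normal), 81.7% (unpooled), 79.8% (log odds ratio), 78.2% (t with 22 df).

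All are within 2 points of 80%, so the figure stands.

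**2. Which contrast it refers to.** Sections 1.1 and 11.1 word the comparison by assignment or arm. The Objective c model in Section 11.2 uses an indicator for randomized group. Section 11.5 analyses patients as assigned. Together these make 15% versus 7.5% the ITT contrast.

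**3. Size of a possible as-treated bias (illustration).** Assumptions, none from the documents except the 10% and 20% edges of the intermediate band: half the patients have 10% FN risk and half 20%; PP-CSF use is 90% in one group and 10% in the other; every override follows risk; no covariate adjustment. Per unit of each group:

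- PP-CSF default: treated are 0.5 at 20% and 0.4 at 10%; untreated are 0.1 at 10%.
- No-PP-CSF default: treated are 0.1 at 20%; untreated are 0.4 at 20% and 0.5 at 10%.

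If PP-CSF has no effect:

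- Treated FN = 0.5×0.20 + 0.4×0.10 + 0.1×0.20 = 16% (total weight 1.0).
- Untreated FN = 0.1×0.10 + 0.4×0.20 + 0.5×0.10 = 14%.
- As-treated: PP-CSF appears to add 2.0 points.
- ITT: 15% versus 15%. Complier estimate: 0 / 0.80 = 0.

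If PP-CSF halves FN risk:

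- As-treated: 14.0% − 8.0% = 6.0 points.
- ITT: also 14.0% − 8.0% = 6.0 points.
- Complier estimate: 6.0 / (0.90 − 0.10) = 7.5 points, the true effect of receipt.

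**4. Precision of the complier estimate.** Estimate = ITT risk difference / difference in use, and SE = ITT SE / difference in use, treating the difference in use as known. FN rate = 15% × (1 − 0.5 × use), effective n 287.2 per group, t(22) = 2.074. Use levels are assumptions. The 75% and 7% are Section 11.1's Intervention figures for high- and low-risk patients, borrowed only to extend the range.

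| Use, PP-CSF / no-PP-CSF default | FN rates | ITT SE (points) | Complier SE (points) | 95% half-width (points) |
|---|---|---|---|---|
| 95% / 5% | 14.63% vs 7.88% | 2.62 | 2.62/0.90 = 2.9 | 6.0 |
| 90% / 10% | 14.25% vs 8.25% | 2.62 | 2.62/0.80 = 3.3 | 6.8 |
| 75% / 7% | 14.48% vs 9.38% | 2.70 | 2.70/0.68 = 4.0 | 8.2 |

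Estimate and SE are divided by the same number, so the test statistic does not change: at 90%/10%, 6.0/2.62 and 7.5/3.28 are both about 2.3.

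**The case against.** **As-treated is only a sensitivity analysis, and confounding can be adjusted for.** Section 7.3 says comorbid factors are collected, and Section 11.2 adjusts its primary models and lists many FN risk factors as subgroups. This stands in part. Adjustment reduces the bias for recorded factors but not for unrecorded reasons for an override. The 2.0-point figure is therefore an unadjusted worst case and does not measure the bias in an adjusted analysis.

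**A complier estimate cannot tell ineffective PP-CSF from an ignored default.** This stands: a null ITT result gives a null complier result with a wider interval. What shows whether the default was followed is PP-CSF use by assigned group. That use is already an endpoint (Section 10.1b), but the Objective a models in Section 11.2 cover only high- and low-risk patients, so the intermediate-risk comparison deserves explicit mention. The complier estimate adds an effect size and interval for receipt that are free of override selection.

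**The method is fragile here.** This also stands. FN is counted over 6 months, and a default in the order set could also change later-cycle CSF or antibiotic use, which would break the assumption. The exposure is defined inconsistently too: Sections 7.1 and 11.2 time PP-CSF from the initial dose, Section 10.1b from cessation of therapy. Section 11.6 would code missing PP-CSF as zero. The fix has to deal with these points.

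**Conclusion.** This is a low-cost improvement to consider, not an error in the primary analysis. Section 11.5's only effect estimate that accounts for non-compliance is open to confounding by indication, and a randomization-based alternative is available. That overrides can follow patient risk is an inference from Sections 2.0, 7.1 and 7.3. The documents do not show how often it happens, so the size of any bias is unknown.

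A reader might go further and infer that Objective c is underpowered, on the view that 50% is a per-patient drug effect that changed orders will dilute. The documents do not support that. The contrast is between assigned groups, and no PP-CSF use figure is given for intermediate-risk patients, so any loss of power rests on assumed use levels. Section 11.1 also cites effects well above 50%: the one prospective intermediate-risk trial achieved a 90% reduction, and a systematic review "found an FN rate reduction ranging from 17% to 78" per cent. The planning ICC was doubled as well, since "the ICC was estimated to be 0.01 although statistically significantly greater than zero". The plan never says outright that its 50% is net of changed orders, but that is at most a matter of wording.

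**What to change.** Keep ITT as primary, and keep the as-treated analysis and the crossover comparison. In Section 11.5, add for Objective c:

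> PP-CSF use by assigned group will be reported beside the ITT result. A supportive complier-average (instrumental-variable) FN risk difference will be estimated, with component assignment as the instrument, observed first-cycle PP-CSF as the exposure, and component-level clustering with a small-number-of-clusters correction. One definition of PP-CSF will be used throughout. The estimate will also be shown excluding patients with missing PP-CSF data. It assumes that the default affects 6-month FN only through first-cycle PP-CSF. The as-treated result will be labelled as open to confounding by indication.

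The timing definitions in Sections 7.1, 10.1b and 11.2 must be reconciled first; which one applies is for the study team. Optionally, a sentence in Section 11.1 can state that the 50% is the ITT reduction net of changed orders.

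The cost is one paragraph, one tabulation and one supportive model on first-cycle CSF data already collected (Section 10.1b). Sample size, primary analysis and conduct do not change, so the fix remains usable although the document is marked closed effective April 2020. It should be dated and, if possible, adopted before FN results by assigned group are examined.

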The specific objectives of this study address two vital evidence gaps in real world practice. This pragmatic study is designed to compare outcomes of PP-CSF use in community practice as currently managed by physicians and clinic staff (usual care) with care that includes a protocol-based, guideline-informed standing PP-CSF order system. The intent of the first study aim is to align PP-CSF prescribing with clinical evidence, where the benefit to patients is likely to be highest. The second specific aim will evaluate the effectiveness of PP-CSF in modern, intermediate-risk chemotherapy regimens, for which there is currently an evidence gap. The design of this study is innovative in that it generates evidence on an important patient-level clinical question within the context of evaluating the effectiveness of a system-level cancer care delivery intervention. Given the documented variation in CSF prescribing and attendant impact on patient outcomes, this pragmatic trial has the potential to provide substantial benefit to many of the 275,000 breast, lung and colorectal cancer patients who receive myelosuppressive chemotherapy each year. (38,39,40)

Cohort Study

The cohort study will provide a parallel observational study of CSF use in community practice as heterogeneous prescribing protocols in the usual care arm will make comparison difficult. The cohort study serves several specific purposes. First, while it is known that some practices and systems have implemented electronic order entry for CSF prescribing, the degree to which these order systems adhere to guidelines, apply to relevant patient populations, or are impacting CSF prescribing are not known. Some systems will be similar enough to the study intervention to render component sites ineligible for the randomized control trial. The **S1415CD** Study Team at the SWOG Statistical Center would like to see how the study approach compares to these sites. Second, this will allow tracking of trends in CSF prescribing over time, comparing the impact of the stakeholder-driven intervention with the others, both in terms of their effectiveness, and how they affect trends in CSF use and related outcomes over time. Finally, the cohort study will facilitate understanding of post-randomized control trial implementation of the intervention if it is effective.

Inclusion of Women and Minorities

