What a physician will see if they prescribe an intermediate risk regimen depends on their study arm. If a component is randomized to include standing orders for PP-CSF for all intermediate risk regimens, default PP-CSF orders will appear on the screen in the same way as the default orders for high-risk regimens. If a component is randomized to not include standing orders for PP-CSF for intermediate-risk regimens, the screen will function in the same way as for low-risk regimens. The alert text will be modified to be specific to the intermediate risk classification of the regimen and the randomized assignment.

Order System- Paper

Paper ordering systems will have the same basic design as the EMR modification but will differ in the implementation strategy, as shown below in [Figure 4](#).

INCLUDE CSF by default
 
DOSE-DENSE AC HIGH risk of FN; PP-CSF recommended
 
Height: _____ Weight: _____
 
Chemotherapy Orders:
 
Doxorubicin 75 mg/m² x _____ m²= _____ mg Cyclophosphamide 600 mg/m² x _____ m² = _____ mg
 
Growth Factors: Pegfilgrastim 6 mg subcutaneous
 
Additional Orders: Saline 1000 mL
	
EXCLUDE CSF by default
 
VINORELBINE LOW risk of FN; PP-CSF not recommended
 
Height: _____ Weight: _____
 
Chemotherapy Orders:
 
Vinorelbine 25 mg/m² x _____ m²= _____ mg
 
Additional Orders: Saline 1000 mL

---	--

[Figure 4](#)

The treating physician may change an individual patient's orders from what is specified by following standard procedures for changing a prescription order when adding or removing CSF. The specific procedures will depend on the EMR and local component preference.

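### The 90% power for Primary Objective b takes no account of the half of the Intervention components that have no default PP-CSF for intermediate-risk patients; on the plan's own rates power is about 68-78% at ICC 0.02

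*Combined protocol and SAP*

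**What the plan says.** The opening paragraph of Section 11.1 promises "at least 90% power to detect a 50% reduction in Primary Objective b". Step 2 defines the effect as a relative reduction "measured by the odds ratio) over both high and intermediate risk groups", comparing 24 Intervention with 8 Usual Care components, and gives 90% power "to detect a 50% reduction in FN events among high and intermediate risk patients in components randomized to the guideline-based PP-CSF order Intervention" versus Usual Care. For high-risk patients the assumed rates are 25% and 12.5%.

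Step 1 divides the same 24 components for Objective c: "12 components randomized to PP-CSF and 12 components to no PP-CSF among intermediate risk patients". The FN rates are 15% without PP-CSF and 7.5% with it. Section 7.2 confirms what the second group means in practice. At a component "randomized to not include standing orders for PP-CSF for intermediate-risk regimens, the screen will function in the same way as for low-risk regimens", so CSF is left out by default.

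Section 11.2b analyses Objective b with one two-level term, Intervention versus Usual Care, so both halves of the Intervention arm enter together. Section 11.7 expects the relative effect of Intervention versus Usual Care to be equal in high- and intermediate-risk patients, and points to an intermediate-risk analysis with 80% power. Table 2 heads its 80% column Primary Obj b and its 90% column Primary Obj a, while the text gives 80% to Objective c and 90% to Objective b.

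**The concern.** Intermediate-risk patients are 50 of every 80 patients counted for Objective b, and half of those in the Intervention arm are at components assigned to no default PP-CSF. So about 31% of the Intervention patients in this test (25 of 80) carry the plan's untreated rate by design. Section 11.1 does not carry this into the effect size for Objective b, and nothing elsewhere in the plan does so.

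Objective b is one of three primary objectives. A non-significant result would be read as coming from a test with a 10% chance of missing the planned effect. If the plan's own inputs give a 22-32% chance, such a result could reflect dilution built into the design and be mistaken for evidence against the order system.

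**Working it through.** **Inputs (Section 11.1).** Two-sided alpha 0.05 (stated in Step 1, taken to apply to Step 2). 8 Usual Care and 24 Intervention components, 90 patients each. Risk mix 30/50/20, so m = 27 + 45 = 72 high- and intermediate-risk patients per component. ICC 0.02 for planning; 0.01 as estimated from the earlier study. Assumption not in the plan: Usual Care intermediate-risk FN is 15%, the plan's rate without PP-CSF.

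**Effective sample size.** Design effect = 1 + (72 − 1) × 0.02 = 2.42. Usual Care: 8 × 72 / 2.42 = 238. Intervention: 24 × 72 / 2.42 = 714.

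**Expected rates.**
- Usual Care: (30 × 25% + 50 × 15%) / 80 = 18.75%.
- Intervention, split left out: 18.75% / 2 = 9.375%.
- Intervention, with split: intermediate risk (7.5% + 15%) / 2 = 11.25%; overall (30 × 12.5% + 50 × 11.25%) / 80 = 11.72%. Reduction 1 − 11.72/18.75 = 37.5%; odds ratio 0.575.

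**Formulas.** With d = |p1 − p2|, SEu the unpooled and SEp the pooled standard error:
- unpooled z: Φ(d/SEu − 1.96)
- pooled z: Φ((d − 1.96 SEp)/SEu)
- t: noncentral t, 30 df, noncentrality d/SEu
- arcsine and log-odds: the usual normal approximations

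Example with the split: d = 0.0703, SEu = 0.0280, d/SEu = 2.51; Φ(2.51 − 1.96) = 70.9%, and 68.0% with t.

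| Scenario (72 per component) | t | unpooled | pooled | arcsine | log-odds |
|---|---|---|---|---|---|
| No split, 50% rate reduction, ICC 0.02 | 90.9% | 92.5% | 95.5% | 95.5% | 96.9% |
| No split, overall OR 0.5 (10.34%), ICC 0.02 | 83.4% | 85.8% | 90.0% | 89.6% | 91.9% |
| Split, ICC 0.02 | 68.0% | 70.9% | 76.5% | 74.9% | 77.9% |
| Split, ICC 0.01 | 82.4% | 84.7% | 88.4% | 87.9% | 90.1% |

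The first two rows reproduce the plan's 90%. Across Table 2 (ICC 0, .01, .02, .03) the t version without the split gives 96/94/91/88%, against the printed 98/94/90/86%. The same formulas give 78-82% for Objective c in every row (12 versus 12 components, 15% versus 7.5%), which matches the printed 80% column.

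**Table 2 rows with the split** (80% of 48, 62, 90 and 168 per component): 79-87%, 73-82%, 68-78% and 64-74%.

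**Simulation.** 20,000 runs with component-level tests (equal-variance t / Welch). With the split: 72% / 64% at ICC 0.02 and 84% / 79% at ICC 0.01. Without it: 95% / 90% and 99% / 97%. The split adds between-component variation that the design effect leaves out.

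**Sensitivity at ICC 0.02, with the split.**
- OR 0.5 within each risk group (Intervention 12.58%): 56-65%.
- 20% of Usual Care intermediate-risk patients already on PP-CSF with FN halved (Usual Care 17.81%): 57-67%. At 40% (16.88%): 45-53%.
- PP-CSF effect of 90% in intermediate and 50% in high risk: 9.84%, a 47.5% reduction, 88-95%.
- Reduction needed for 90% power: about 44-49% overall. The two risk groups contribute equally to Usual Care events (30 × 25 = 50 × 15), so a common PP-CSF effect e gives 0.5e + 0.25e = 0.75e overall. The required e is therefore about 58-66%.

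**Intermediate risk alone, Intervention versus Usual Care** (15% versus 11.25%, a 25% reduction; 45 per component, ICC 0.02): 24-29%.

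**The case against.** The strongest reply is that the statement is conditional: 90% power holds for a true 50% reduction, so nothing has been miscalculated. That is right about the formula. But Step 2 presents 50% as the planned effect, and the plan's rates and randomisation do not yield it.

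Second, the shortfall depends on inputs. The 15% Usual Care rate is an assumption. Section 2.0 itself says that "heterogeneous prescribing protocols in the usual care arm will make comparison difficult", and any existing PP-CSF use in that group lowers power further. A larger PP-CSF effect would restore it: Section 11.1 cites a 90% reduction in one intermediate-risk trial, yet the plan chose 50%. At ICC 0.01 the most favourable formula reaches 90%, but the plan states its power at 0.02 and gives the reason: "We are using 0.02 to protect against underestimation of the ICC".

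Third, how the printed column was produced is unknown. The log-odds formula fits the Objective c column best but, without the split, gives more than the printed values for Objective b. This stands. It does not help the 90%, because with the split every formula falls below 78% at ICC 0.02.

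Fourth, the 12.5% high-risk rate may itself be optimistic. Step 2 plans high-risk CSF use rising only from 40% to 75%. Halving FN in users, with 25% as the Usual Care rate, implies 25 / (1 − 0.4 × 0.5) = 31.25% in non-users and 31.25 × (1 − 0.75 × 0.5) = 19.5% at Intervention components. With the split the overall reduction is about 23% and power 32-38%. This also stands: 68-78% is conditional on the plan's 12.5%.

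Finally, the three-way comparison in Section 11.2b and the interaction test in Section 11.7 help interpretation, but neither restates the power. The protocol is marked closed from 04/15/2020, and randomised sites took only intermediate-risk patients from December 2, 2019, so the realised risk mix may differ from 30/50/20. That does not make the stated power consistent with the design.

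**Conclusion.** The concern holds. The 90% for Objective b rests on a 50% reduction that the 12/12 split rules out at the plan's own rates. The implied reduction is 37.5%, with power of about 68-78% at ICC 0.02 and 82-90% at ICC 0.01 for 90 patients per component; simulation is somewhat lower (64-72% and 79-84%). This rests on the plan's 50% PP-CSF effect, its 12.5% high-risk Intervention rate, its risk mix, and an assumed 15% intermediate-risk rate in Usual Care. The less favourable readings of Usual Care practice and high-risk uptake examined above lower the figure.

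Section 11.7 has the same fault: the inputs imply reductions of about 50% in high and 25% in intermediate risk. The 80% it mentions matches Objective c, which compares PP-CSF with no PP-CSF and not Intervention with Usual Care. The Table 2 column labels are a separate labelling error.

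**What to change.** 1. **Section 11.1, Step 2.** State that 12 of the 24 Intervention components have no default PP-CSF for intermediate-risk patients. Add that, with a 15% intermediate-risk rate assumed in Usual Care, the design rates are 18.75% in Usual Care and 11.7% in the Intervention arm (high 12.5%, intermediate 11.25%), a 37.5% reduction (OR 0.575). Give power at 90 patients per component as about 68-78% at ICC 0.02 and 82-90% at ICC 0.01, depending on the formula. Say that it is lower if Usual Care intermediate-risk patients already receive PP-CSF, and that 90% at ICC 0.02 needs an overall reduction of about 44-49%. Change the opening paragraph of 11.1 to match.
2. **Section 11.7.** Replace the expectation of equal relative effects with about 50% (high) and 25% (intermediate). Say that the 80%-power analysis is Objective c, and that Intervention versus Usual Care in intermediate-risk patients has about 24-29% power.
3. **Table 2 and its introductory sentence.** Relabel the power columns as Objective c (80%) and Objective b. Restate Objective b as about 79-87%, 73-82%, 68-78% and 64-74% for ICC 0, .01, .02 and .03. Note that the .01 row uses 62 patients per component, which is why it differs from the 82-90% in the text.

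The cost is wording and a less favourable stated power for a primary objective. Sample size, data collection and the planned test do not change.
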